## **10.5. Clinical Laboratory Evaluation**

Laboratory data including Chemistry, Hematology, and urinalyses will be summarized by treatment and visit for the Safety Population. Descriptive summaries of actual values and changes from baseline will be presented by study visit and last assessment for each clinical laboratory analyte and for each treatment group. 95% confidence intervals will be presented for change from baseline.

Laboratory values will be displayed in the data listings with their corresponding normal ranges, and those values that are outside the normal range will be flagged. For each laboratory analyte shifts in assessments of abnormality from baseline to each scheduled time point will be presented in shift tables.

Results of urine drug screens and pregnancy tests will be presented in listings.

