- d Nasal exam will only be performed at Visit 6 if any abnormality on exam at Visit 5 or any report of a nasal cavity AE
- e Chemistry panel only: triggered serum osmolality will be measured from same specimen if sodium is below the lower limit of normal
- f Urinalyses, hematology and chemistry labs will only be repeated at Visit 6 if clinically significant findings were observed at Visit 5
- Women of childbearing potential only: screening serum pregnancy test will be analyzed at Central laboratory; consecutive urine pregnancy tests will be conducted on-site at every subsequent study visit
- h Urine drug test: cocaine, phencyclidine (PCP), barbiturates, amphetamines, cannabis, and opiates
- i C-SSRS: Columbia Suicide Severity Rating Scale
- MSI-BPD: McLean Screening Instrument for Borderline Personality Disorder
- k E-diary training will be conducted at Visit 1 (Screening Visit) and Visit 2 (Treatment) and will be repeated at Visits 3 and 4. E-diary is collected at Visit 5
- Patients will start completing their e-diary the day after their Screening Visit.
- Study drug administration training performed at Visit 2 in addition to dispensation of study drug
- n PGIC: Patient Global Impression of Change
- ° HADS: Hospital Anxiety and Depression Scale
- p MIDAS: Migraine Disability Assessment questionnaire
- q MSQ: Migraine-Specific Quality of Life Questionnaire v2.1
- r CSFQ-14: Changes in Sexual Functioning Questionnaire Short-Form
- Pharmacogenomics should be drawn at Baseline but if it is not drawn, drawing at a subsequent visit is allowed.
- Placebo Response training will be conducted in the form of a video that patients watch at Visit 1. At subsequent visits (V2-V5), training will be conducted via a paper script that the site staff reviews with the patient.

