# 6.7 Clinical Laboratory Tests

# 6.7.1 Laboratory Parameters

Patients will be in a seated or supine position during blood collection. Clinical laboratory tests will include the following:

Table 1. List of Laboratory Tests

Serum Chemistry				
Alkaline phosphatase	Creatine kinase (CK)			
Alanine aminotransferase (ALT; SGPT)	Glucose			
Aspartate aminotransferase (AST/SGOT)	LDH			
Blood urea nitrogen (BUN)	Phosphorus			
Bilirubin (direct and total)	Potassium			
Calcium	Sodium (serum osmolality will also be tested if Sodium is below the lower limit of normal)			
Carbon dioxide (CO 2 )	Protein (total)			
Chloride	Triglycerides			
Creatinine	Uric Acid			
Hematology				
Hematocrit (Hct)	Mean corpuscular volume (MCV)			
Hemoglobin (Hgb)	Platelet count			
Mean corpuscular hemoglobin (MCH)	Red blood cell (RBC) count			

Serum Chemistry				
MCH concentration (MCHC)	WBC differential			
Other				
Thyroid Stimulating Hormone (TSH)	Hemoglobin A1c (HbA1c)			

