#### 7.2.8 Special Considerations

# 7.2.8.1 Adverse Events of Special Interest

Since IN administrations of agents can cause significant irritation of nasal mucosa, events of nasal irritation will be followed closely during the study and considered an AE of Special Interest. Investigators should monitor for tissue changes or lesions in the visualized nasal mucosa on nasal exam, and for pain or discomfort anywhere in the nasal cavity, sinuses or oropharynx.

Because intranasal administration of oxytocin can result in a transient, albeit short-lived and minor, rise in systemic oxytocin levels, there will be specific monitoring for the potential adverse effects of supraphysiological levels of oxytocin in plasma. It should, however, be noted that with intranasal administration and the proposed oxytocin dosing regimens, sustained and clinically relevant plasma oxytocin levels are not expected. It is out of an abundance of caution that close monitoring for potential safety signals will be carried out.

Theoretically, if substantial and sustained concentrations in plasma are achieved, plasma oxytocin may activate off target vasopressin receptors leading to antidiuretic effects. Thus, AEs that may involve changes in blood volume, blood pressure, and specific electrolyte disturbances (hyponatremia) will be AEs of special interest, e.g., new onset edema, hypervolemia, increased blood pressure, ECG changes related to cardiac hypertrophy or arrhythmia.

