## **8. GENERAL ANALYSIS AND REPORTING CONSIDERATIONS**

Descriptive summaries will be provided where appropriate for each of the primary and secondary variables. In general, tables will summarize data by treatment group and visit.

Continuous, quantitative variable summaries will include the number of patients (N) with non-missing values, mean, standard deviation, median, minimum, and maximum.

Categorical, qualitative variable summaries will include the frequency and percentage of patients who are in the particular category. In general, the denominator for the percentage calculation will be based upon the total number of patients in the study population for the treatment group unless otherwise specified.

Unless otherwise specified, baseline values are defined as the last non-missing measurement prior to the first dose of study drug. Change from baseline will be defined as the post-baseline visit value minus the baseline value.

For continuous endpoints where treatment groups are compared via linear models with the difference in LS means, the effect size will be calculated and included as a summary statistic using the difference in LS means and its standard error, transformed to a standard deviation. Study day is defined as assessment date – first dose date +1 for dates after the first dose date and assessment date – first dose date for dates prior to the first dose.

All analyses will be performed using SAS® Software version 9.4 or later.

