## 10. SAFETY EVALUATION

### 10.1. Overview of Safety Analysis Methods

All safety analyses will be completed for the Safety Population. All safety data will be tabulated and listed. No formal statistics or imputation will be performed for the safety analysis. The analysis of safety assessments in this study will include summaries of the following safety and tolerability data collected for each patient:

- Extent of exposure
- Incidence of Adverse Events
- Changes from baseline in clinical laboratory results
- Changes from baseline in vital signs
- Changes from baseline in electrocardiograms
- Monitoring suicidality using the Columbia Suicide Severity Rating Scale (C-SSRS)
- Changes from baseline in the HADS scores
- Changes from baseline in the CSFQ-14

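### SAP 10.5 averages serum osmolality like any other analyte although it is run only on low-sodium specimens, so its means and changes from baseline cannot be compared between arms (minor reporting flaw)

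*SAP*

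**What the plan says.** **When osmolality is measured.** Protocol Table 1 (Section 6.7.1) gives osmolality no row of its own. It appears in the sodium entry: "Sodium (serum osmolality will also be tested if Sodium is below the lower limit of normal". Footnote e of the protocol's Schedule of Assessments says the same: "triggered serum osmolality will be measured from same specimen if sodium is below the lower limit of normal". The SAP schedule (Appendix 15.1) repeats the footnote, and that is the SAP's only mention of osmolality.

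**How laboratory data are summarized.** SAP 10.5 sets one rule for everything: "Descriptive summaries of actual values and changes from baseline will be presented by study visit and last assessment for each clinical laboratory analyte". It adds "95% confidence intervals will be presented for change from baseline" and "For each laboratory analyte shifts in assessments of abnormality from baseline to each scheduled time point will be presented in shift tables". It makes no exception for a test that is run only after another result is abnormal.

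**Baseline and missing values.** SAP Section 8 states that "baseline values are defined as the last non-missing measurement prior to the first dose of study drug". SAP 10.1 adds: "No formal statistics or imputation will be performed for the safety analysis".

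**The safety concern.** Protocol 7.2.8.1 discusses possible antidiuretic effects and says: "Thus, AEs that may involve changes in blood volume, blood pressure, and specific electrolyte disturbances (hyponatremia) will be AEs of special interest".

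**The concern.** Set together, these rules produce an osmolality table with three defects.

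- **Selected means.** The mean at a visit covers only patients whose sodium was low at that visit. If the drug lowers sodium, it changes who is tested. The active and placebo means then describe differently selected groups, both held just under the same cut-off.
- **Almost no change from baseline.** A baseline osmolality exists only if sodium was low at V1 or V2. A patient whose sodium first falls on treatment, the case of most interest, has no baseline. That patient drops out of the change rows and cannot be placed in the shift table.
- **A distorted last-assessment row.** A patient's last osmolality can be a triggered Week 4 value even though sodium was normal at Weeks 8 and 12.

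At stake is a table on a named safety topic in which two similar means could be taken as reassurance.

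There is also a smaller gap. SAP 10.5 plans no once-per-patient count of new low sodium across all on-treatment visits. The adverse event tables do not fully fill it: Protocol 6.7.3 records only clinically significant laboratory abnormalities as AEs, and SAP 10.4 spells out only nasal irritation as an AE of special interest.

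**Working it through.** The documents state no sodium or osmolality figure, so there is none to reproduce. The textual part follows from the passages above. The arithmetic below only sizes the selection.

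**Inputs**
- From the documents: osmolality exists only if sodium < LLN; chemistry is scheduled for all patients at V1 to V5; two pre-dose draws (V1, V2); no imputation; about 100 patients per arm (Protocol 10.2), used only as a scale.
- Assumed: sodium normal with mean 140 mmol/L; SD 2.0 or 2.5; LLN 135 or 136; within-patient correlation 0.5; osmolality = 2 × sodium + 10 + independent noise; drug lowers sodium by 2 mmol/L. The true difference in mean osmolality is then 2 × (-2) = -4.0 mOsm/kg.

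**Step 1: mean osmolality among triggered specimens.** With z = (LLN - μ)/SD,

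E[sodium | sodium < LLN] = μ - SD × φ(z)/Φ(z).

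For LLN 135 and SD 2.5:
- Placebo: z = (135 - 140)/2.5 = -2.0; φ/Φ = 0.05399/0.02275 = 2.373; sodium 140 - 2.5 × 2.373 = 134.07; osmolality 278.13.
- Active: z = (135 - 138)/2.5 = -1.2; φ/Φ = 0.19419/0.11507 = 1.688; sodium 138 - 2.5 × 1.688 = 133.78; osmolality 277.56.
- Difference -0.57 instead of -4.0; attenuation 1 - 0.57/4.0 = 86%.

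The same formula in all four settings:

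| LLN, SD | Tested per 100, placebo / active | Triggered mean, placebo / active | Difference | Attenuation |
|---|---|---|---|---|
| 135, 2.0 | 0.6 / 6.7 | 278.71 / 278.25 | -0.46 | 88% |
| 135, 2.5 | 2.3 / 11.5 | 278.13 / 277.56 | -0.57 | 86% |
| 136, 2.0 | 2.3 / 15.9 | 280.51 / 279.90 | -0.61 | 85% |
| 136, 2.5 | 5.5 / 21.2 | 279.88 / 279.16 | -0.72 | 82% |

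**Step 2: scale-free check.** Put the LLN at the 2nd percentile and shift sodium by -1 SD. Low-sodium incidence rises from 2.0% to 14.6%. The mean sodium of triggered specimens moves from -2.42 to -2.57 SD. Only 0.15 of 1 SD, or 15%, is visible.

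**Step 3: patients with a change from baseline.** A patient needs low sodium before dosing and again at the visit. Let P2 be the probability that one given pre-dose draw and the post-dose draw are both low, and P3 the probability that both pre-dose draws and the post-dose draw are all low. Because a triggered V1 value can serve as baseline when V2 is not triggered, the probability is 2 × P2 - P3.

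For LLN 135 and SD 2.5, per 100:
- Active: 2 × 1.122 - 0.285 = 1.96
- Placebo: 2 × 0.405 - 0.137 = 0.67

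Over the four settings the count is 0.5 to 5.4 per 100 active and 0.1 to 2.2 per 100 placebo. Using V2 alone (P2) gives 0.3 to 3.3 and 0.1 to 1.4.

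**Step 4: what remains visible.** Sodium, measured in everyone, shows the full -2.0 mmol/L in its own table. The number of osmolality results also separates the arms, as the second column shows.

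**The case against.** The strongest reply is that nothing important depends on this table.

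- **Sodium is reported without selection.** It is in the chemistry panel for all patients at V1 to V5. SAP 10.5 gives it means, changes with 95% intervals and shift tables. This stands.
- **Counts of low sodium are partly planned.** A reader might infer that the SAP has no count of treatment-emergent low sodium. The documents do not support that: the sodium shift table shows movement from normal to low at each scheduled visit, provided its categories separate low from high. Only the roll-up across visits, and its link to osmolality, are missing.
- **The osmolality N carries information.** SAP Section 8 requires the number of non-missing values, and for osmolality that is the low-sodium count. This stands, although nothing directs the reader to the N rather than the mean.
- **The table is inferred.** SAP 10.5 never names osmolality. The table follows only from the rule covering each analyte. That is fair, but the rule has no exception and a programmer applying it would produce the table.
- **The motive is not stated.** A reader might infer that osmolality was added because of Protocol 7.2.8.1. That section does not mention osmolality, and no passage gives the reason.
- **Safety analysis is descriptive.** No decision rule uses osmolality. This limits the consequence to reporting.

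**Conclusion.** A minor reporting flaw, but the rule is wrong as written. Applied to osmolality, SAP 10.5 yields means selected on a post-randomization outcome that are not comparable between arms, and change-from-baseline rows that are nearly empty. Under the assumptions above, differences in means are attenuated by 82-88%. The exact percentages rest on those assumed sodium and osmolality distributions and the assumed 2 mmol/L effect. That the means are selected, and that new cases have no change from baseline, follows from the trigger rule alone.

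A reader might go further and conclude that the trial cannot show an antidiuretic effect. The documents do not support this. The osmolality means are attenuated rather than blank, their N differs between arms if the drug lowers sodium, and sodium itself is fully reported.

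**What to change.** Amend SAP 10.5 as follows.

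1. Exempt triggered serum osmolality from by-visit and last-assessment means, change-from-baseline intervals and shift tables. List its values with the sodium result from the same specimen.
2. Use sodium for the between-arm description.
3. Add one table by arm: the number and percentage of patients with at least one on-treatment sodium below the LLN and none below it before dosing, over all patients with at least one on-treatment sodium result. Beneath it, give the number of those patients who also had osmolality below its reference range.

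The on-treatment results should be those from V3 to V5 or early termination. Chemistry at V6 is repeated only after clinically significant V5 findings, so it would bring selection back in. With that limit, the denominator does not depend on any trigger.

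**Cost.** SAP wording and one extra table; no new sample, assay or visit. The downside is that no osmolality means are reported.

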## **10.6. Vital Signs, Electrocardiograms, Physical Findings, and Other Observations Related to Safety**

### **10.6.1. Vital Signs**

Descriptive summaries (mean, SD, median, minimum, and maximum) of actual values and changes from baseline at each assessment time point and last assessment will be calculated for vital signs including weight, body mass index, body temperature, pulse rate, systolic blood pressure and diastolic blood pressure. 95% confidence intervals will be presented for change from baseline. Vital sign values, including abnormal values, will be listed.

### **10.6.2. Electrocardiograms (ECGs)**

Descriptive summaries (mean, SD, median, minimum, and maximum) of actual values and changes from baseline at each assessment time point and last assessment will be calculated for each electrocardiogram parameter. 95% confidence intervals will be presented for change from baseline. Additionally, the number and percentage of patients with normal, abnormal/not clinically significant, and abnormal/ clinically significant ECG interpretations will be summarized at each assessment time point and last assessment. Percentages will be out of the number of subjects in the safety population. Electrocardiogram values, including clinical interpretation values, will be listed.

### **10.6.3. Physical Examinations**

Physical examination data will be presented in a data listing.

### **10.6.4. Other Safety Measures**

#### **10.6.4.1. Columbia Suicide Severity Rating Scale (C-SSRS)**

Based on the C-SSRS results, the overall number of patients with lifetime and/or current suicidal ideation (by item and category), suicidal behavior (by item and category), or self-injurious

behavior at the screening and baseline visit will be summarized by visit and treatment group. Additionally, the overall number of patients with any suicidal ideation or behavior (by type and in total) or self-injurious behavior while on-treatment will be provided by treatment group. Patients will only be counted once for on-treatment ideation and on-treatment behavior, at the worst-case response for each item.

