# Efficacy Mean change from Baseline in the Migraine Disability Assessment (MIDAS) Test total score at Week 12. Secondary **Endpoints:** Mean change from Baseline in the Hospital Anxiety and Depression Scale (HADS) total score at Week 12. Mean change from Baseline in patient-rated Changes in Sexual Functioning Questionnaire Short-Form (CSFQ-14) total score in males and in females, analyzed separately, at Week 12. **Exploratory** Proportion of patients experiencing a $\geq$ 75% reduction in the number of **Endpoints:** migraine headache days from the last 28 days of Baseline to the last 28 days of treatment in each treatment group. • Proportion of patients with fewer than 14 headache days or fewer than 8 migraine headache days per 4 weeks over the 12-week period. Mean change from Baseline in number of headache free days from the last 28 days of Baseline to the last 28 days of treatment. • PGIC rating (1-7) at Week 12 Safety Change in suicidality using the C-SSRS scale **Endpoints:** Incidence of adverse events (AEs) Changes from Baseline in clinical laboratory tests • Changes from Baseline in vital signs Change from Baseline in ECG parameters Clinically significant change(s) in physical examination findings Clinically significant change(s) in nasal examination findings Changes from Baseline in the Hospital Anxiety and Depression Scale (HADS) total score at Week 12 Changes from Baseline in patient-rated Changes in Sexual Functioning Questionnaire Short-Form (CSFQ-14) in males and in females, described separately The modified intention-to-treat population (mITT), defined as all randomized Statistical patients who receive at least 1 dose of study drug and have at least one post-Methods: Baseline, evaluable month (that is, at least one of the three 28-day periods has at least 14 non-missing e-diary entries), will be used as the primary population for all efficacy analyses. The sample size and power calculations for this study are based on the analysis of the primary efficacy outcome variable: mean change in the number of migraine headache days from the last 28 days of Baseline to the last 28 days of treatment in each treatment group. **Efficacy Analysis** The primary efficacy endpoint of change from Baseline will be analyzed using a mixed-effects model of repeated measures (MMRM) with fixed

effects of treatment, month, baseline value, treatment by month interaction,

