## 6.9.2 Columbia- Suicide Severity Rating Scale

The C-SSRS is a questionnaire developed by researchers at Columbia University to assess and track suicide risk and behavior. This scale is intended to be used by individuals who have received training in its administration. The questions contained in the Columbia Suicide Severity Rating Scale are suggested probes. Ultimately, the determination of the presence of suicidal ideation or behavior depends on the judgment of the individual administering the scale.

Two versions of this questionnaire will be utilized in this study. At Visit 1, the "Baseline/Screening" questionnaire will be administered, and the recall periods will be "lifetime" and "within the past 6 months" for suicidal ideation and "within the past 1 year" for suicidal behavior. Patients whose responses are indicative of suicidal ideation with any method, intent, and/or plan (e.g., Type 3, 4 or 5 suicidal ideation) within the past 6 months or a history of suicidal behavior within the past year will be excluded from participation, with recommended referral for intervention as appropriate.

At all subsequent visits (Visits 2, 3, 4, 5, and 6), the "Since Last Visit" version of the questionnaire will be administered, and the recall period on this will be "since the last visit". Note that if there has been an increase in suicidal ideation or suicidal behavior, appropriate intervention should be prescribed.

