## 10.7.3 Safety Analysis

All safety analyses will be completed for the Safety Population. All safety data will be tabulated and listed. No formal statistics will be performed for the safety analysis.

Adverse events that occur between the time written informed consent is provided and the start of study drug administration will be considered pretreatment AEs. Adverse events that start during or after study drug administration, or AEs with an onset prior to study drug administration that worsen after study drug administration will be considered TEAEs. All AEs will be coded using MedDRA, and the incidence of TEAEs will be summarized overall and by preferred term and system organ class for each treatment group. Incidence of TEAEs will also be summarized by severity and relationship to study drug. Serious AEs, TEAEs involving the nasal passages, and TEAEs leading to discontinuation of study drug will also be summarized.

Actual values and changes from Baseline for clinical laboratory test results, ECG parameters, vital signs, HADS scores, and CSFQ-14 scores will be summarized by treatment group and

visit using descriptive statistics (n, mean, SD, median, minimum, and maximum). The number of patients with baseline and treatment-emergent suicidal ideation and/or suicidal behavior, based on the C-SSRS, will be summarized by treatment group. For each laboratory test, individual patient values will be listed and values outside of the standard reference range will be flagged.

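### The SAP's C-SSRS table counts any on-treatment ideation or behaviour without reference to the patient's own baseline, so it is not the treatment-emergent count the protocol plans, and the place of Visit 6 is left unstated

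*SAP*

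**What the plan says.** The protocol synopsis lists "Change in suicidality using the C-SSRS scale" among the safety endpoints, and Protocol 10.5.1 includes changes in C-SSRS scores in its primary safety endpoints. For the analysis, Protocol 10.7.3 plans that the number of patients with "baseline and treatment-emergent suicidal ideation and/or suicidal behavior, based on the C-SSRS, will be summarized by treatment group"; the synopsis says the same.

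SAP 10.6.4.1 plans two summaries. The first covers lifetime and/or current ideation, suicidal behaviour and self-injurious "behavior at the screening and baseline visit will be summarized by visit and treatment group". The second covers the period after dosing starts: "the overall number of patients with any suicidal ideation or behavior (by type and in total) or self-injurious behavior while on-treatment will be provided", separately for each arm. The counting rule for the second is: "Patients will only be counted once for on-treatment ideation and on-treatment behavior, at the worst-case response for each item".

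Under Protocol 6.9.2 the C-SSRS is given at all six visits. Visit 1 uses the screening form, with lifetime and recent recall (6 months for ideation, 1 year for behaviour). Visits 2 to 6 ask about the time since the previous visit.

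**The concern.** Pairing baseline with treatment-emergent cases implies separating what a patient brought into the trial from what appeared or got worse after dosing began. The SAP's two summaries cannot do that, because they are separate marginal counts with no link within the patient. Someone with the same Type 1 ideation before and after randomisation is an on-treatment case in the SAP table, exactly like someone who developed it on study drug. A move from Type 1 to Type 2 cannot be told apart from Type 2 ideation that was there all along.

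The SAP handles comparable safety data differently. Adverse events are treatment-emergent on first onset or worsening (10.3), laboratory abnormalities get shift tables from baseline (10.5), and HADS and CSFQ-14 are summarised as change from baseline (10.6.4.2, 10.6.4.3).

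A second gap concerns timing. SAP 10.6.4.1 does not say when the on-treatment period ends. The Visit 6 C-SSRS covers an interval after dosing has stopped, and the early-termination C-SSRS may cover days off drug. At stake is whether a reader of the tables can identify new cases in a safety measure where few are expected.

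**Working it through.** The documents give no figure for this point, so there is none to reproduce. The check is a comparison of texts, a day count and an illustration.

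**1. Who is affected.** Protocol 6.9.2 and 8.1 exclude patients with Type 3-5 ideation in the past 6 months or suicidal behaviour in the past year. Protocol 8.2 screen-fails anyone with either between Visit 1 and Visit 2. (Exclusion 5 joins its two examples differently in the synopsis and in Section 4.2, and the wording should be reconciled; I rely on 6.9.2, 8.1 and 8.2, where either is enough.) On-treatment behaviour and Type 3-5 ideation are therefore new relative to those recall periods, and since the SAP counts by type they will be visible. Type 1-2 ideation is not named in any of these rules, and stable depression is allowed (Exclusion 10), so such patients can enter unless the investigator judges them at increased risk. The loss is confined mainly to Type 1-2 ideation.

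**2. Visit 6 against the adverse-event window.** Visit 6 is nominally Day 99 and Visit 5 Day 85; the treatment period runs to Day 84.
- 99 − 85 = 14 days after Visit 5; 99 − 84 = 15 days after Day 84.
- With the 4-day window: 103 − 84 = 19 days.

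An adverse event is treatment-emergent up to 30 days after the last dose (Protocol 7.1.2, SAP 10.3). Visit 6 lies inside that window but after dosing. On a literal reading of *on-treatment* it is out; on the adverse-event convention it is in. The SAP does not say which applies to the C-SSRS.

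**3. Size, on assumed rates.** Take 100 per arm (the planned number). Let b be the share entering with Type 1-2 ideation, s the share of those in whom it persists unchanged, and e the share of the others who develop ideation. Worsening among those with ideation at entry is set to zero.
- Treatment-emergent = 100 × (1 − b) × e
- SAP count = 100 × (1 − b) × e + 100 × b × s

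With e = 0.02 and s from 0.25 to 0.75:

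| b | Treatment-emergent | SAP count, s = 0.25 | SAP count, s = 0.75 |
|---|---|---|---|
| 0 | 2.0 | 2.0 | 2.0 |
| 0.02 | 1.96 | 2.46 | 3.46 |
| 0.05 | 1.9 | 3.15 | 5.65 |
| 0.10 | 1.8 | 4.3 | 9.3 |

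For b = 0.05, s = 0.75: 100 × 0.95 × 0.02 = 1.9, plus 100 × 0.05 × 0.75 = 3.75, gives 5.65.

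**4. Effect on the comparison of arms.** Suppose 5 per 100 in each arm carry stable ideation throughout and the drug adds 3 new cases per 100. The SAP table shows 8 against 5; the treatment-emergent count shows 3 against 0. The excess is 3 per 100 either way. What changes is the ratio (8/5 = 1.6 in the SAP table) and whether the new cases can be identified.

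**The case against.** The strongest reply is that little is lost. The C-SSRS is collected at every visit, and SAP 10.1 promises that all safety data go into tables and listings. Baseline results are tabulated by arm in the same paragraph as the on-treatment counts, so the groups can be compared. Randomisation should balance carried-over ideation, and the excess between arms is unchanged in the illustration. The post-baseline form asks only about the time since the last visit, so lifetime history is not carried forward. Clinically relevant findings at a visit are also to be treated as adverse events (Protocol 7.2.1). Finally, the protocol never defines *treatment-emergent* for the C-SSRS; the new-or-worsened definition is written for adverse events.

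Most of this stands, and it rules out two stronger readings that a reader might infer. One is that the suicidality endpoint is not measured. It is: the data exist, the serious categories are excluded at entry, and counts are by type. The other is that Visit 6 results will be left out. The SAP is silent rather than exclusionary: the period is undefined, the general sections have tables by visit and window early-termination data as far as Week 14 (SAP 8 and 8.1.3), and 10.1 covers all safety data.

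What does not stand is the step from comparable groups to a treatment-emergent count. Two marginal counts cannot show which patients are new or worse, and the baseline table may mix lifetime with current recall. The missing definition in the protocol is a reason for the SAP to supply one. Counting every case present on treatment does not do so.

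**Conclusion.** The point holds in a limited form. SAP 10.6.4.1 states a rule that yields a different count from the one the protocol plans. The difference bears mainly on Type 1-2 ideation already present at entry. It is zero if nobody enters with such ideation, and on the assumed rates above it can roughly double or triple a small count (1.9 against 3.15 to 5.65 at 5% prevalence). Those rates are illustrative; the documents supply none. The difference between arms is not biased in the illustration, which assumes equal carry-over in each arm; the harm is that new or worsened cases cannot be picked out in the summary.

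Separately, the handling of Visit 6 is unspecified, which is a gap in definition and not evidence of omission. The SAP's section on changes from the protocol is redacted, so whether the departure was declared cannot be judged. The change is worth making because this is a named safety endpoint and the remedy is small.

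**What to change.** In SAP 10.6.4.1, keep the existing screening, baseline and on-treatment counts and add three things.

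1. A shift table by arm, from the worst pre-dose category (the Visit 1 recent-recall period together with Visit 2) to the worst category after the first dose.
2. From the same derivation, the number of patients per arm with new or worsened ideation, and the number with new behaviour.
3. A definition of the on-treatment period, stating how an early-termination assessment made after a lapse in dosing is classified, with Visit 6 tabulated explicitly, either within that period or as a separate follow-up column. Either is workable provided it is fixed before unblinding.

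The cost is one derivation and one table. No assessment, visit or form changes, because all the data are already collected.
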